9.3 POPULATIONS FOR ANALYSES

The analysis dataset will include:

- Intention-to-Treat (ITT) Analysis Dataset (i.e., all randomized participants)
- Safety Analysis Dataset: defines the subset of participants for whom safety analyses will be conducted (e.g., participants who took at least one dose of study intervention)
- Other Datasets that may be used for sensitivity analyses (e.g. subgroups by dose, sex, age, baseline labs, adherence)

9.4 STATISTICAL ANALYSES

9.4.1 GENERAL APPROACH

The primary intention-to-treat analysis uses Williams' ANOVA-based test to find, with high statistical power (90%), the minimum effective dose of vitamin E that improves the per-person primary endpoint, defined as the percentage relative change in ALT from baseline over 24 weeks of treatment with either vitamin E or matching placebo. The sample size justification allows for 10% missing data using a complete-case Williams' test on the non-missing data; however, if the percentage of patients with missing data on the primary endpoint is greater than 10%, multiple imputation modeling at each step in the Williams' test procedure will be used to include all randomized patients in the determination of the step-by-step p-values needed for the Williams' test dose-finding procedure.

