9.2 SAMPLE SIZE DETERMINATION

The primary endpoint is the relative change in ALT at week 24 from baseline [i.e., (ALT at baseline – ALT at week 24)/ALT at baseline]. There are three vitamin E treatment groups: 133.4 mg/day, 266.8 mg/day, 533.6 mg/day and one placebo group. The primary analysis is intention-to-treat analysis of minimum effective dose using Williams' test of mean 24-week relative change in ALT. If the percentage of patients with missing follow-up data on the primary endpoint is greater than 10%, multiple imputation using chained equations method with 50 imputations modeling will be used to impute missing values; otherwise complete-case analysis will be used.

Among patients in PIVENS with baseline ALT ≥ 60 U/L, the mean 24-week relative change in ALT was 40% in the vitamin E (800 IU/day) group and 20% in the Placebo group. The Mean (SD) of the vitamin E – placebo difference in relative change (%) was -20% (31%). Using this estimate as the clinically meaningful difference, the trial has 90% power to detect a significant minimum effective dose given a sample size of 200 patients (50 per group with equal allocation) given a 2-sided Type I error of 5%, missing data rate of 10% and using Williams' test for minimum effective dose (MED) (Williams 1971, Williams 1972) obtained from PASS 2019 software (PASS 2019 Power Analysis and Sample Size Software (2019). NCSS, LLC. Kaysville, Utah, USA, ncss.com/software/pass).

The testing for minimum effective dose starts by comparing the 24-week relative change in ALT in each of the 3 dose groups with the placebo group using critical values obtained from Williams' test for MED. (Critical values will be obtained using SAS PROBMCM function.) Williams' test assumes the same or increasing efficacy with increasing dose; therefore, if the mean change at a dose level is less in absolute value than the mean change in a lower adjacent dose category, the groups are combined for statistical comparison. The lowest dose that is significantly different from placebo is declared the MED. By definition, all doses greater than the MED are also significantly different from placebo.

Sample size estimates for varying sizes of the treatment effect are given below given the same assumptions as above.

24-week relative change in ALT			Sample size	
Vitamin E	Placebo	Vitamin E – Plbo	No. / group	Total
48%	20%	28%	25	100
44%	20%	24%	34	136
40%	20%	20%	50	200
36%	20%	16%	76	304

32%	20%	12%	135	540
28%	20%	8%	303	1212

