9.4.2 ANALYSIS OF THE PRIMARY EFFICACY ENDPOINT(S)

- Intention-to-Treat (ITT) Analysis Dataset

The primary endpoint is 24-week relative change in serum ALT, defined as the ALT obtained at the 24-week visit minus ALT at the baseline visit divided by ALT at baseline [i.e., $(\text{ALT at baseline} - \text{ALT at week 24}) / \text{ALT at baseline}$]. The change in serum ALT is measured on a continuous scale and is a single endpoint. The Williams' ANOVA-based test for minimum effective dose of vitamin E starts by comparing the primary endpoint between the lowest vitamin E dose of 133.4 mg (200IU) vs. placebo. If significantly better ($p < 0.05$) using the 5th percentile from the Williams' test, then 133.4 mg is declared the minimum effective dose and no other comparisons are made; If the previous step is not significantly better, then the 266.8 mg (400 IU) dose is compared vs placebo. If significantly better ($p < 0.05$) using the 5th percentile from of the Williams' test, then 266.8 mg (400IU) is declared the minimum effective dose and no other comparisons are made. If the previous step is not significantly better, the 533.6 (800IU) mg dose is compared vs placebo. If significantly better ($p < 0.05$) using the 5th percentile from the Williams' test, the 533.6 (800IU) mg is declared the minimum effective dose and no other comparisons are made. If the previous step is not significantly better, then declare that no minimum effective dose for vitamin E was found. The primary analysis will present the (up to) 3 p-values from the Williams' test steps above and, only if the William's

test finds a minimum effective dose, the primary analysis will also include the estimated difference and 95% confidence interval for 24-week percentage relative change vs. baseline, comparing the minimum effective 24-week dose group vs placebo. As sensitivity analyses, the 3 separate comparisons of each vitamin E dose group vs placebo with estimates and 95% confidence limits be presented. Sensitivity analyses will include use of robust regression to down-weight the effect on the Williams' test minimum effective dose selection of influential outliers in the relative ALT change from baseline measures. Other sensitivity analyses may be used to balance potential effects on results of confounders not balanced out by randomization, as judged by the trial Data Safety and Monitoring Board.

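### The 90% power in section 9.4.1 is for one dose, 20 points better than placebo, to reach significance; the chance of naming the correct minimum effective dose is a different quantity, and often a lower one

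*Combined protocol and SAP*

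**What the plan says.** The primary objective (sections 1.1 and 3) and the primary hypothesis (section 9.1) concern which of three doses is the minimum effective dose (MED). Section 9.4.2 makes the primary result the name of one dose, or a statement that none was found. It tests 200 IU first and moves up only on failure: "If the previous step is not significantly better, then the 266.8 mg (400 IU) dose is compared vs placebo", and so on to 800 IU.

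Power appears in three places. Section 1.1 gives only a figure of 90% and the name of the method. Section 9.2 says "the trial has 90% power to detect a significant minimum effective dose given a sample size of 200 patients". Section 9.4.1 goes furthest and says the test is used "to find, with high statistical power (90%), the minimum effective dose of vitamin E".

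The effect behind the figure comes from PIVENS patients with baseline ALT of at least 60 U/L: "the mean 24-week relative change in ALT was 40% in the vitamin E (800 IU/day) group and 20% in the Placebo group", with an SD of 31%. Every row of the sample-size table also has a single vitamin E mean. No mean is given for 200 or 400 IU. Section 9.2 adds that a dose whose mean falls below that of the next lower dose is pooled with it.

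**The concern.** Naming the right dose takes more than one significant contrast. No lower, ineffective dose may be declared on the way up, and no lower, effective dose may be missed. A calculation with one vitamin E mean and one placebo mean covers neither event. So 90% cannot in general be the probability of finding the MED, which is how section 9.4.1 words it.

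The trial's product is a dose. Someone planning the next study could take 90% as the reliability of the declared MED. Section 2.3.3 places the value of the trial in learning whether a lower dose suffices. If response rises gradually with dose, the sample size can by itself push the declared dose upward, and section 9.4.2 does not warn that an undeclared lower dose has not been shown ineffective.

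**Working it through.** **Inputs.** Placebo 20%, vitamin E 40%, SD 31 (section 9.2); 50 per group and 10% missing, hence 45 evaluable per arm (sections 9.2 and 9.4.1); pooling of out-of-order doses (section 9.2); ascending order of tests (section 9.4.2). Sidedness differs between sections. Section 9.2 has "given a 2-sided Type I error of 5%, missing data rate of 10" per cent, while section 9.4.2 has "using the 5th percentile from the Williams' test, then 133.4 mg is declared the minimum effective dose", which reads as a one-sided 5% point. Both were run.

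**Reproducing the plan's figure.** n = 2 × SD² × (t + 1.2816)² / difference², where t is the three-dose Williams critical value (simulated with 176 df: 1.746 for one-sided 5%, 2.045 for 2.5% per side).

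- One-sided 5%: 2 × 31² × (1.746 + 1.2816)² / 20² = 44.05, so 45 evaluable; 45 / 0.9 = 50 per group, as printed.
- The other rows, with the large-sample value 1.739 and division by 0.9, give 24.9, 33.8, 76.1, 135.3 and 304.4, against 25, 34, 76, 135 and 303 in the table.
- Power of one contrast at 45 per arm: noncentrality 20 / (31 × √(2/45)) = 3.06. Noncentral t gives 90.5% at t = 1.746 and 84.4% at t = 2.045.

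The 90% is therefore one dose against placebo, at the one-sided 5% Williams value.

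**Probability of naming the correct dose.** Simulation with 45 per arm, SD 31, pooled variance and 400,000 replicates per scenario. Effects over placebo at 200/400/800 IU are assumptions, because the plan gives none for the two lower doses. Pooled means were tested upward (three-dose or step-specific critical values) and by step-down. Raw means were tested upward only. The two-sided column spans all variants.

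| Effects | Correct dose | One-sided 5%, pooled | One-sided 5%, raw means | Two-sided 5% |
|---|---|---|---|---|
| 0, 0, 20 | 800 IU | 85.3-85.7% | 82.3-83.2% | 80-82% |
| 0, 20, 20 | 400 IU | 84.1-84.7% | 85.9-86.4% | 79-82% |
| 20, 20, 20 | 200 IU | 88.1-90.0% | 90.5-91.9% | 80-86% |

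In the first row, pooled, about 9.5% of trials declare nothing and about 5% name a lower, ineffective dose: 100 − 9.5 − 5 = 85.5%.

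**Graded responses** (pooled, one-sided 5%), percentage of trials naming 200 / 400 / 800 IU / none:

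- 6.7, 13.3, 20: 22-25 / 39-40 / 28-30 / 8
- 5, 10, 20: 14-16 / 28-29 / 47-48 / 9

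At two-sided 5% the most often named dose under the second shape (800 IU) reaches about 54%.

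**The case against.** The case for leaving the text alone has several good parts.

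- Section 9.2's wording can fairly be read as power to declare some dose. With pooling at one-sided 5%, some dose is declared in about 90-97% of trials under the three on/off shapes. That stands, so the overstatement lies in section 9.4.1. Section 1.1 makes no claim about finding the MED.
- If all three doses have the full 20-point effect, the correct dose is named in about 88-90% of trials (pooled), so 90% is fair there. That stands too.
- When only 800 IU works, the shortfall is largely the 5% error rate that the plan prints beside its power. This explains the gap of about 5 points, but it does not make 90% the probability of finding the MED.
- Section 9.4.2 already plans estimates with confidence limits for all three doses, as sensitivity analyses, and nowhere says that an undeclared dose will be called ineffective. This reduces the risk of misreading without removing it.

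A reader might go further and infer three things that the documents do not support. The first is that the sample size is miscalculated; it reproduces. The second is that the chance of success is as low as 82%. That figure for an MED of 800 IU at one-sided 5% arises when raw arm means are tested, contrary to section 9.2's pooling rule. The third is that the lowest active dose will be found only 15-45% of the time. This counts any effect at 200 IU as effective, whereas section 9.2 uses 20 points as the clinically meaningful difference. On that yardstick 800 IU is the correct answer under both graded shapes and is named in about 28-30% and 47-48% of trials. The plan does not say which definition applies.

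**Conclusion.** The point holds in a limited form. The 90% is a correct figure attached to the wrong quantity. It is the power for one dose with a true 20-point advantage (in practice 800 IU) to beat placebo, and only at one-sided 5%. At the two-sided 5% stated in section 9.2 it is about 84%.

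Against 90%, the shortfall in naming the correct dose (pooled, one-sided 5%) is about 4 to 6 points when the effect starts at 400 or 800 IU, and negligible to 2 points when all doses work fully. For graded responses it is large: whichever dose is called the MED, it is named in at most about 48% of trials at one-sided 5%, or about 54% at two-sided 5%. These results rest on 45 evaluable per arm, SD 31 and the assumed dose-response shapes. The graded result shows how sensitive the conclusion is to shape; it is not a forecast. Nothing here argues against the design or the number of patients.

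**What to change.** 1. Reconcile the two-sided 5% in section 9.2 with the 5th percentile in section 9.4.2, since the power to be printed depends on it.
2. In section 9.4.1, and for clarity in section 9.2, replace the claim of 90% power to find the MED with the power for a dose truly 20 points better than placebo to be declared significant, and state the sidedness: about 90% at one-sided 5%, about 84% at two-sided 5%. In section 1.1, define the 90% entry to match.
3. Next to it, print the simulated probability of naming 200 IU, 400 IU, 800 IU or none for the final procedure, with pooling, under stated shapes: effect at 800 IU only, plateau from 400 IU, plateau from 200 IU, and graded. Say what effect size counts as effective when scoring the graded case.
4. In section 9.4.2, state that failure to declare a lower dose will not be reported as evidence that it is ineffective, and that the three dose-versus-placebo estimates with confidence limits will be reported together with the declared MED.

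The cost is some rewording and one short simulation. N stays at 200, and the endpoint and treatments are untouched. The downside is a less favourable headline figure.

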9.4.2 ANALYSIS OF THE PRIMARY EFFICACY ENDPOINT(S)

- Intention-to-Treat (ITT) Analysis Dataset

The primary endpoint is 24-week relative change in serum ALT, defined as the ALT obtained at the 24-week visit minus ALT at the baseline visit divided by ALT at baseline [i.e., $(\text{ALT at baseline} - \text{ALT at week 24}) / \text{ALT at baseline}$]. The change in serum ALT is measured on a continuous scale and is a single endpoint. The Williams' ANOVA-based test for minimum effective dose of vitamin E starts by comparing the primary endpoint between the lowest vitamin E dose of 133.4 mg (200IU) vs. placebo. If significantly better ($p < 0.05$) using the 5th percentile from the Williams' test, then 133.4 mg is declared the minimum effective dose and no other comparisons are made; If the previous step is not significantly better, then the 266.8 mg (400 IU) dose is compared vs placebo. If significantly better ($p < 0.05$) using the 5th percentile from of the Williams' test, then 266.8 mg (400IU) is declared the minimum effective dose and no other comparisons are made. If the previous step is not significantly better, the 533.6 (800IU) mg dose is compared vs placebo. If significantly better ($p < 0.05$) using the 5th percentile from the Williams' test, the 533.6 (800IU) mg is declared the minimum effective dose and no other comparisons are made. If the previous step is not significantly better, then declare that no minimum effective dose for vitamin E was found. The primary analysis will present the (up to) 3 p-values from the Williams' test steps above and, only if the William's

test finds a minimum effective dose, the primary analysis will also include the estimated difference and 95% confidence interval for 24-week percentage relative change vs. baseline, comparing the minimum effective 24-week dose group vs placebo. As sensitivity analyses, the 3 separate comparisons of each vitamin E dose group vs placebo with estimates and 95% confidence limits be presented. Sensitivity analyses will include use of robust regression to down-weight the effect on the Williams' test minimum effective dose selection of influential outliers in the relative ALT change from baseline measures. Other sensitivity analyses may be used to balance potential effects on results of confounders not balanced out by randomization, as judged by the trial Data Safety and Monitoring Board.

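### Sections 9.2 and 9.4.2 describe different primary procedures for the minimum effective dose, and 9.4.2 as worded does not hold the stated 5% error

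*Combined protocol and SAP*

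**What the plan says.** Section 9.4.2 sets the decision rule for the primary endpoint. The 200 IU arm is compared with placebo first, "using the 5th percentile from the Williams' test". If it is significantly better, "then 133.4 mg is declared the minimum effective dose and no other comparisons are made". If not, 400 IU is tested against placebo in the same way, and then 800 IU. The section says nothing about combining dose groups and does not require a higher dose to be significant before a lower one is named.

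Section 9.2 describes the same test differently. Each of the three doses is compared with placebo. Efficacy is assumed not to fall as dose rises, and a dose that looks worse than the adjacent lower dose is merged with it. The outcome is then stated in two sentences: "The lowest dose that is significantly different from placebo is declared the MED" and "By definition, all doses greater than the MED are also significantly different from placebo". Section 9.2 also gives the Type I error as two-sided 5% and says that "the trial has 90% power to detect a significant minimum effective dose" with "50 per group with equal allocation".

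Section 9.4.1 refers to p-values obtained at successive steps of the procedure, but gives neither the order of the steps nor the extent of pooling.

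**The concern.** The usual Williams procedure starts at the highest dose and moves down only while each step is significant. A false claim then has to get past the first test, so the error rate is that of one test. Section 9.4.2 runs the other way: a dose that fails is followed by another attempt at the next dose, up to three attempts in all, each at roughly 5%. It also stops without examining the higher doses, so the assurance in 9.2 about those doses does not follow from it.

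Naming the MED is the trial's only primary objective. If two sections lead to different decisions from the same data, the choice between them should be made before treatment codes are broken.

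**Working it through.** **Inputs.** From 9.2: difference 20 percentage points, SD 31, four equal arms of 50, 10% missing data, power 90%. Evaluable patients per arm: 50 × 0.9 = 45. Pooled-variance df: 4 × 45 − 4 = 176. Williams critical values for 1, 2 and 3 doses, upper-tail 5%, are 1.652, 1.724 and 1.748. They were found by simulation, so the third decimal is approximate.

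**Reproducing the plan's sample size.** With c₃ the 3-dose critical value, n = 2 × [SD × (c₃ + z₀.₉₀) / difference]².

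- Upper-tail 5%: 2 × [31 × (1.748 + 1.282) / 20]² = 44.1, so 45 per arm; 45 / 0.9 = 50. This matches the plan exactly.
- Power at 45 per arm: the standard error is 31 × √(2/45) = 6.535; 20 / 6.535 − 1.748 = 1.312; Φ(1.312) = 0.905.
- The other rows of the 9.2 table come out at 26, 35, 77, 137 and 307 per group, against the stated 25, 34, 76, 135 and 303.
- Upper-tail 2.5% (a true two-sided 5%): c₃ = 2.047 gives 53.2, so 54 per arm; 54 / 0.9 = 60. Power at 45 per arm is Φ(3.060 − 2.047) = 0.84.

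Two things follow. The sample size matches the 3-dose critical value, which belongs to a test of 800 IU with all three doses in play. It also matches a one-sided 5% point, not the two-sided 5% that 9.2 states.

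**False-MED rate.** One million trials per scenario were simulated with normal data, equal variances, 45 per arm and the 1-, 2- and 3-dose critical values at successive steps.

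| Procedure | No effect, upper 5% | Only 800 IU works (20 points), upper 5% | No effect, upper 2.5% |
|---|---|---|---|
| Upward, no pooling | 10.7% | 8.2% | 5.7% |
| Upward, pooling among doses reached | 10.7% | 8.2% | 5.7% |
| Upward, pooling over all three first | 5.3% | 5.2% | 2.6% |
| Downward, pooling over all three first | 5.0% | 5.0% | 2.5% |

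A bound shows that 10.7% is plausible. The unpooled tail areas beyond 1.652, 1.724 and 1.748 are about 5.0%, 4.3% and 4.1%, which sum to 13.4%; the shared placebo arm makes the tests correlated and brings the total down.

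The first two rows agree for a simple reason. Pooling among doses reached acts only when the next dose looks worse than one that has already failed, and then neither the pooled nor the unpooled comparison passes the larger critical value.

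With pooling over all three doses the means are already in order, so the test statistics rise with dose. Upward and downward testing then agree in 99.7% of null trials, and in all of them if one common critical value is used.

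**The statement about higher doses.** Share of declared MEDs (upward testing, upper-tail 5%) with at least one higher dose not significant:

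| Pooling | No effect | All doses 20 points |
|---|---|---|
| None | 68% | 13% |
| Among doses reached | about 57–58% | 3% |
| Over all three first | 6% (0.3% of all trials) | 0.8% |

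**The case against.** The strongest reply is that 9.4.2 names Williams' test at every step and 9.2 says what that test involves, including merging doses that fall out of order. Read together, the two sections could mean pooling over all three doses, and direction then hardly matters: the error is about 5.3% and the statement about higher doses is very nearly true. This reply stands as far as it goes. A reader might infer that the primary rule certainly doubles its error, or that the sentence in 9.2 is simply false; the documents support neither. They also do not exclude the worse reading. Section 9.2 merges a dose with its lower neighbour without saying when, and in a sequence that begins at 200 IU the first step has no lower active dose to merge with.

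The size also depends on the tail. With 2.5% in the upper tail, even the literal reading of 9.4.2 gives about 5.7%.

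Two further inferences should be resisted. One is that the plan reports an estimate only for a dose that reaches significance. Section 9.4.2 also commits to all three comparisons with placebo, with 95% limits, as sensitivity analyses. The other is to judge the rule by a case in which 200 IU works and higher doses do not; that contradicts the ordering assumption stated in 9.2.

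**Conclusion.** The point holds as an inconsistency with a conditional cost. Followed literally, 9.4.2 does not control the error at 5%: the false-MED rate is about 10.7% at one-sided 5% points and about 5.7% at 2.5% points. Under pooling over all three doses, which neither section states, the rates are about 5.3% and 2.6%. The 9.2 statement about higher doses does not follow from 9.4.2, but is nearly correct under that pooling.

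These figures assume normal data with equal variances, 45 evaluable per arm, and step-specific critical values, which 9.4.2 does not spell out. Multiple imputation was not simulated. The wording should be settled before unmasking, because it defines the primary result.

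**What to change.** Use one description in 9.2 and 9.4.2:

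1. Compute order-restricted means over all three doses before any test.
2. Test 800 IU against the 3-dose Williams critical value. If it is not significant, stop and declare no MED.
3. If it is significant, test 400 IU against the 2-dose value, and then 200 IU against the 1-dose value, stopping at the first step that is not significant.
4. Declare as MED the lowest dose reached with every higher dose significant. The 9.2 sentence about higher doses is then true by construction.
5. State whether the 5% is one-sided or two-sided, and give the power that belongs to that choice.

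At one-sided 5% points this gives 5.0% error and about 90.5% power when only 800 IU has the 20-point effect, with 50 per group unchanged. At 2.5% upper-tail points power at 50 per group is about 84%, and 90% would need 60 per group.

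The change is to wording only, with the same data and the same critical-value function. Some of the upward rule's chance of naming an MED is given up: at 2.5% points with a 20-point effect at every dose, that chance is 92.9% instead of 96.9%.
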